9.4 Randomization (RCT Cohort Only)

When it is determined the subject has met all inclusion criteria and no exclusion criteria (including echocardiographic exclusion criteria), the subject may undergo the procedure and if the subject is targeted for the RCT phase, will be randomized in a 1:1 fashion to either the CLAAS or Control device according to a computer-generated randomization scheme. Randomization will be stratified by investigational site.

Randomization shall be within 90 days of informed consent. The LAA occlusion procedure shall take place within and including 14 days from the date of randomization.

9.5 Index Procedure

Trained Conformal representatives may be present during the CLAAS Implant procedure. Representatives from the manufacturer of the Control Device may be present during the Control implant procedure. The TEE Baseline assessments will include review of the echocardiographic selection criteria to confirm these criteria have been met. In addition, LAA measurements will be obtained and reviewed to confirm sizing criteria in accordance with the CLAAS and Control System IFU.

Platelet count, HCT/Hgb lab testing must be collected within 48 hours prior to the index procedure.

- **9.5.1 Randomized Cohort:** The LAA occlusion procedure shall take place within 14 Days from the date of Randomization.
- **9.5.2 Roll-In Cohort:** The LAA occlusion procedure shall take place within 90 days of obtaining informed consent.

9.5.3 Pre-Procedure Medical Therapy

Pre-procedure oral anticoagulation should be managed as per site protocol. Warfarin should be discontinued in accordance with site standard of care practices including INR levels on the day of the procedure.

The following loading doses should be administered prior to the index procedure:

Aspirin

- ASA 81-100 mg (administered 1 day prior to procedure), or
- ASA 325 mg (chewed 1 hour prior to procedure)

Antibiotic Prophylaxis

 Pre-procedure antibiotic for endocarditis prophylaxis should be administered prior to the procedure as per local standard of care.

9.5.4 Intraprocedural Medical Therapy

Intraprocedural anticoagulation with heparin should be administered per physician standard practice in accordance with published guidelines and local standards of care, with a goal of maintaining an activated clotting time (ACT) of 250-350 sec throughout the procedure. The highest and lowest intraprocedural ACT measurements shall be recorded in the CRF for all subjects.

Total heparin dose and prophylactic antibiotics shall be recorded in the subject's medical record and recorded on the eCRF.

9.5.6 Transseptal Puncture

Percutaneous femoral vein access and transseptal puncture should be performed per physician standard practice using a standard commercially available transseptal access system.\

9.5.7 Procedural Imaging

Procedural ultrasound imaging will be performed by a qualified physician (e.g. Physician echocardiologist) who is *not* the implanting physician.

A procedural ultrasound evaluation (e.g., TEE imaging), prior to introducing the device/delivery system into the body, will include evaluation for pericardial effusion, presence of LAA thrombus, and LAA sizing, and is required to confirm eligibility and evaluate baseline status. If subject is randomized, but the subject eligibility is not achieved after ultrasound evaluation, the subject shall

be considered a Screen Failure and will be followed for 45 days to evaluate safety. If subject is not randomized and subject eligibility is not achieved during ultrasound evaluation, the subject may be exited from the study with no additional follow-up required.

This protocol includes specific requirements for procedural TEE imaging acquisition in accordance with the Imaging Core Lab requirements. The details of this TEE Imaging Acquisition Protocol are provided in the Study Manual of Procedures. Imaging for core lab assessment shall document the following:

- Baseline assessment (prior to device introduction),
- Intra-Procedural (pre and post tether release) assessments, and
- Final procedural assessment (post implant delivery system removal).

All procedural angiographic and echocardiographic images must be uploaded using the image submission guidelines outlined in the Study Manual of Procedures.

At any time during the study, echocardiographic imaging obtained during a repeat procedure or for diagnostic purposes should also be uploaded for analysis.

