8.8.1 Roll-In Population

A Roll-In ITT subject is an individual who signs an ICF, is assigned to the Roll-In Cohort by the site and has an implant procedure attempted. For this population, an implant procedure attempt (ITT established) is defined when the LAAO Access Sheath is introduced into the body.

If an implant procedure is attempted without an implant placed, the subject must be followed through the Primary Safety and Efficacy Endpoints (at all visits including 7-days, 45-days, 6-months, 12-months, and 18-months) assessing only: QVSFS, AE Assessment, and Concomitant Medication Assessment. These assessments can be conducted via telehealth/phone call. These subjects will not be required to have subsequent protocol mandated imaging and will not be required to follow the medication requirements. If a subject in the Roll-in population experiences a suspected stroke or systemic embolism, the subject should be brought in for an Unscheduled Visit (in-person clinic visit) for assessment per the Schedule of Assessments matrix. After the 18-Month visit, these subjects will have completed all required study assessments.

Subjects who are scheduled for a roll-in procedure, but no longer meet eligibility criteria and do not have a procedure attempt (i.e., the access sheath never entered the body) will be followed only through 45 days via telehealth/phone call visits. No protocol mandated imaging or medication therapy will be required. After the 45-Day visit, these subjects will have completed all required study assessments and will be classified as Screen Failures.

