8.8.2 Conscious Sedation Population

The Conscious Sedation ITT subject is an individual who signs an ICF, has been assigned to the Conscious Sedation Cohort and has an implant procedure attempted. For this population, an implant procedure attempt (ITT established) is defined when the CLAAS Delivery Catheter is introduced into the body.

If an implant procedure is attempted without an implant placed, the subject must be followed through the Primary Safety and Efficacy Endpoints (at all visits including 7-days, 45-days, 6-months, 12-months, and 18-months) assessing only: QVSFS, AE Assessment, and Concomitant Medication Assessment. These assessments can be conducted via telehealth/phone call. These subjects will not be required to have subsequent protocol mandated imaging and will not be required to follow the medication requirements. If a subject in the Conscious Sedation Population experiences a suspected stroke or systemic embolism, that subject should be

brought in for an Unscheduled Visit (in-person clinic visit) for assessment per the Schedule of the Assessments matrix. After the 18-Month visit, these subjects will have completed all required study assessments.

Subjects who are scheduled for a conscious sedation procedure, but no longer meet eligibility criteria and do not have a procedure attempt (i.e., the CLAAS Delivery Catheter never entered the body) will be followed only through 45 days via telehealth/phone call visits. No protocol mandated imaging or medication therapy will be required. After the 45-Day visit, these subjects will have completed all required study assessments and will be classified as Screen Failures.

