- **Imaging evaluation**, preferably TEE, must be performed in all subjects who left the index procedure with an implanted device.
 - Cardiac CT may be used in lieu of TEE to screen for end point findings, e.g., DRT or >3mm Leak.
 - If a Device Related Thrombus is detected, a TEE is required to confirm the finding as soon as possible (recommended assessment within 2 weeks; at latest, 4-6 weeks from date of original study or at the subject's next follow up visit, whichever is first).
 - If a non-trivial leak is noted, a TEE is required to confirm the finding, as soon as possible (recommended assessment within 2 weeks; at latest, 4-6 weeks from date of original study or at the subject's next follow up visit, whichever is first).
 - Note: A trivial leak is one in which filling is incomplete or is seen on only delayed imaging, with a gap that is ≤1mm.
 - If a non-trivial Pericardial Effusion (defined as effusion measuring >10mm) is detected on Cardiac CT, TTE evaluation is required for quantification.
- Current concomitant medications documentation. If DAPT has been interrupted or terminated, the stop date (and resumption date, if applicable) and the reason for interruption/termination should be recorded.
- Adverse event assessment

Prior to concluding the visit, research staff should also review the follow-up requirements with the subject to help ensure study compliance.

NOTE: Subjects who were withdrawn due to no longer meeting eligibility criteria at the time of the index procedure TEE, but never had a procedure attempt, must be followed through 45-days post procedure for telehealth/phone call visits including 7-days and 45-days (imaging not required and protocol mandated medication therapy not required). After the 45-Day follow-up, these subjects will have completed all required study assessments.

9.10 6-month Follow-up (± 30 days) (Telehealth Visit)

All subjects will have a clinical assessment performed via a telehealth visit (at a minimum) at 6 months (± 30 days), to include the following assessments:

- Questionnaire for Verifying Stroke Free Status (QVSFS) If any question is answered "Yes," a formal neurologic examination and evaluation must be performed by a board-certified neurologist or clinical designee (e.g., neurology fellow).
- Current concomitant medications documentation. If DAPT has been interrupted or terminated, the stop date (and resumption date, if applicable) and the reason for interruption/termination should be recorded.

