Protocol deviations shall be reviewed and reported in the study reports, i.e., Annual Progress Report, as applicable.

12 Safety Reporting

Investigators are responsible for reporting and assessing all adverse events as applicable per protocol and all device deficiencies that could have led to a serious adverse device effect. These events will be documented in the case report forms for the study. In addition, the investigator is responsible for reporting any new and/or updated information related to already reported events. Adverse event collection for the study will occur from the time of randomization in the RCT cohort and at the time of consent for the Roll-In Cohort and Conscious Sedation Sub-Study Cohort.

In this study, subjects should also be encouraged to report adverse events (AEs) spontaneously or in response to general, non-directed questioning. During the study, the subject may volunteer information that resembles an adverse event (AE). If it is determined that an AE has occurred, the investigator should obtain all the information required to complete the AE CRFs.

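### Section 9.5.7 lets a non-randomized subject who fails at the procedural ultrasound leave with no follow-up, while 8.8.1 and the 9.9 NOTE require contact through 45 days for the same roll-in subject

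*Protocol*

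**What the plan says.** Section 9.5.7 requires an ultrasound evaluation before the device or delivery system is introduced, partly to confirm eligibility. It then separates two cases of failure. Randomized subjects are kept for 45 days for safety. For the others the condition is "If subject is not randomized and subject eligibility is not achieved during ultrasound evaluation", and the consequence is that "the subject may be exited from the study with no additional follow-up required".

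Other sections cover subjects who lose eligibility before any attempt:

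- **Section 8.8.1 (roll-in):** subjects whose access sheath was never introduced "will be followed only through 45 days via telehealth/phone call visits" and are then classed as screen failures.
- **Section 8.8.2 (conscious sedation):** the same 45-day rule applies to "Subjects who are scheduled for a conscious sedation procedure, but no longer meet eligibility criteria and do not have a procedure attempt", with the delivery catheter as the marker of an attempt.
- **Section 9.9, NOTE:** subjects found ineligible at the index-procedure TEE "but never had a procedure attempt, must be followed through 45-days post procedure for telehealth/phone call visits including 7-days and 45-days". The NOTE is not limited to randomized subjects.
- **Appendix E, part H, NOTE:** for sub-study subjects with no implant attempt, the 45-day visit is the last one required.

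Section 12 starts adverse event collection "at the time of consent for the Roll-In Cohort and Conscious Sedation Sub-Study Cohort".

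**The concern.** Section 9.5.7 and Section 8.8.1 give opposite instructions for one identifiable person: a consented roll-in subject, brought to the procedure, who is found ineligible on the scan. A site that uses the permission in 9.5.7 does not meet 8.8.1 or the 9.9 NOTE.

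The stake is safety capture. By the time of the procedural TEE these subjects may have had their anticoagulation managed and an aspirin load given (Section 9.5.3), and will usually have been anesthetized or sedated. Section 12.7.1 lists anesthesia risks, including aspiration pneumonia, and airway or esophageal trauma from TEE or intubation. Some of these can declare themselves after the subject has gone home. Roll-in data feed a comprehensive safety summary (Section 8.2.1), so whether such harms are actively sought should not depend on which section the site reads.

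**Working it through.** There is no figure to reproduce; the check is whether the rules apply to the same subject.

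**Step 1. Has a procedure been attempted at the time of the scan?** Section 9.5.7 places the scan before the device or delivery system enters the body. Section 7.4.1 counts both the access sheath and the delivery catheter as parts of the delivery system. Section 8.8.1 defines an attempt by the access sheath and Section 8.8.2 by the delivery catheter. A subject who fails at this scan and goes no further is a no-attempt subject under both definitions.

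**Step 2. Who is non-randomized at that point?** RCT subjects are randomized after eligibility is confirmed, and the procedure follows within 14 days (Section 5, footnote 17; Section 9.4). Roll-in and sub-study subjects are never randomized. Roll-in subjects therefore fall within the literal wording of 9.5.7.

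**Step 3. Required follow-up for a non-randomized subject who fails at the scan with no attempt.**

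| Source | Cohort covered | Required follow-up |
|---|---|---|
| 9.5.7 | any non-randomized subject | none (0 days), exit permitted |
| 8.8.1 | roll-in | remote contact through 45 days |
| 9.9 NOTE | no cohort restriction | contacts at 7 and 45 days |
| 8.8.2 | conscious sedation | remote contact through 45 days |
| Appendix E, part H | conscious sedation | 45-day visit is the last required |

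Section 8.2.1 also gives roll-in subjects the same data collection and follow-up requirements as randomized subjects. Section 9.5.7 is the outlier.

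**Step 4. How directly does 9.5.7 reach the sub-study?** Only indirectly. Sections 9.5.1 and 9.5.2 name the randomized and roll-in cohorts. Appendix E has its own index-procedure and imaging parts with no exit rule. The link is the general statement, in Section 8.2.3 and Appendix E part A, that the sub-study follows all protocol requirements. The two rules specific to the sub-study agree on 45 days for no-attempt subjects, so the conflict is direct for roll-in and secondary for the sub-study.

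**Step 5. What could go unrecorded?** Collection starts at consent in both cohorts (Section 12). Section 12.1 makes serious events, procedure-related events and pre-procedure events reportable, and Section 9.5.8 requires observed events to be entered. An event seen before exit is therefore captured. The gap is limited to events that arise, or become known, after exit.

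**The case against.** The strongest defense is that the sentence was written for someone else. Section 9.5.7 does not name the roll-in or sedation cohorts, and a 14-day limit does not exclude randomization on the day of the procedure. A consented RCT candidate who fails the scan before being randomized could be the intended subject, and exit without follow-up would fit Section 12, which starts RCT event collection at randomization. This is a plausible intention, but the sentence does not state it, and roll-in subjects remain within its wording.

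The defense can also say that 9.5.7 only permits exit, so a site that follows everyone for 45 days complies with every section. That is true. It limits the consequence but does not remove the contradiction.

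Three stronger readings are tempting and are not supported:

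- **That exiting a subject under 9.5.7 breaches Section 12.** Section 12 fixes when collection starts for these cohorts; the passage sets no length of follow-up.
- **That a sedation or airway event before catheter entry would be lost, defeating Objective 3.** Such an event precedes exit and is already reportable. Objective 3 concerns safe delivery of the device, and the sub-study's primary safety components do not include airway or sedation events.
- **That a definite number of subjects would be lost.** With 300 roll-in and 130 sub-study subjects and an assumed failure rate of 2% to 5%, one gets 430 × 0.02 = 8.6 to 430 × 0.05 = 21.5. No failure rate is given. The 130 have their own rule in Appendix E; roll-in alone would give 300 × 0.02 = 6 to 300 × 0.05 = 15. Sections 8.2.1 and 8.3.1 express the 300 as subjects who may be implanted, so it is not clearly the number reaching the scan. Permitted exit is also not certain exit.

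**Conclusion.** The point holds as an inconsistency in the current text. For a roll-in subject who fails at the procedural ultrasound without an attempt, 9.5.7 requires 0 days of follow-up and 8.8.1 and the 9.9 NOTE require 45. For the sub-study the same mismatch exists only through the general compliance clause.

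The consequence is small: possible loss of harms that appear or become known after exit, in subjects outside the primary analysis dataset. Neither primary endpoint test is affected. The number of subjects cannot be derived. The conclusion rests on reading non-randomized literally, which includes roll-in subjects. The neighboring sentence in 9.5.7 on randomized subjects is a separate matter that correcting this one would not settle.

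**What to change.** Reconcile the last sentence of that paragraph in Section 9.5.7 with Sections 8.8.1 and 8.8.2, the 9.9 NOTE and Appendix E part H, so that a single stated follow-up rule governs non-randomized subjects who fail at the procedural ultrasound. A cross-reference from 9.5.7 to the cohort sections would be enough. If the sentence was meant only for RCT candidates who have consented but are not yet randomized, name that group and exclude roll-in and sub-study subjects.

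The cost is one sentence in the next amendment. Aligning 9.5.7 with the other sections would add no contacts beyond those they already require, and no analysis changes.

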9.5.8 Implant Deployment

Implantation of either the CLAAS or Control Implant should be performed as per the manufacturer's IFU.

Procedural details will be captured as appropriate on the procedural worksheets and subsequently recorded on the eCRF. Any Adverse Events or Device Deficiencies observed shall also be recorded in the EDC.

The procedure is considered complete once the last venous access sheath is removed or the subject has been discharged from the catheterization lab, whichever is first.

9.6 Anticoagulation/Antiplatelet Therapy Requirements – CLAAS

9.6.1 Post-Procedure

- If the final **post procedural**, post tether release TEE demonstrates adequate seal (residual leak ≤5mm) and there is no evidence of thrombus, subjects *shall* receive DAPT (ASA 81-100 mg QD and clopidogrel* 75 mg QD) until 45 days post-procedure imaging.
- At **45 days**, if adequate closure has been documented on imaging, DAPT *should* be continued to 6 months, unless deemed unsafe by the subject's physician.
- At **6 months**, if adequate closure has been documented on the 45-day TEE, DAPT should be replaced by monotherapy (ASA 81-100 mg preferred, P2Y12 inhibitor permitted) until 12-month clinical assessment; and is recommended for the duration of the trial (clopidogrel* may be substituted for ASA at the discretion of the subject's physician).
- At **12 months**, if adequate closure has been documented on imaging, medical therapy should be administered based upon institutional standard of care.

NOTE: A substitute P2Y12 inhibitor (i.e., prasugrel, ticagrelor) may be used as per managing physician's judgement. For subjects who are known clopidogrel non-responder an alternative P2Y12 inhibitor should be used.

9.6.2 Additional Considerations:

Inadequate seal: Subjects with inadequate seal (residual leak >5mm) at the post-deployment TEE (or any subsequent TEE or Cardiac CT) should be evaluated for treatment with DOAC and ASA for 4-6 weeks followed by repeat TEE. If inadequate seal persists on TEE, antithrombotic therapy should be considered until seal is confirmed on follow up imaging. Repeat imaging should

be conducted per SOC. Resolution of inadequate seal must be documented on follow up imaging. All additional SOC imaging (TEE or Cardiac CT) should be provided to the Sponsor for Core Lab Review. Antithrombotic therapy should be individualized to the subject based on anatomic (size of leak) and clinical (risk of anticoagulation) considerations.

Device Related Thrombus: If thrombus is detected on the LA surface of the device on the post-procedure TEE (or any subsequent TEE or Cardiac CT), the subject should be evaluated for treatment with OAC (Warfarin or DOAC), and ASA for 4-6 weeks followed by repeat imaging. Repeat imaging should be conducted per SOC or at the patient's next study visit. All additional SOC imaging (TEE or Cardiac CT) should be provided to the Sponsor for Core Lab Review. Antithrombotic therapy should be continued until confirmation of thrombus resolution has been documented on follow up imaging. Antithrombotic therapy should be individualized to the subject based on clinical (risk of anticoagulation) considerations.

9.6.3 Antiplatelet and Oral Anticoagulant Therapy Requirements (CONTROL):

Control subjects should be treated according to the marketed LAAO device manufacturer's Instructions for Use.

9.6.4 Endocarditis Prophylaxis

Appropriate endocarditis prophylaxis is recommended for 6 months following device implantation. The decision to continue beyond 6 months is at the discretion of the principal investigator or operator.

9.7 Pre-discharge Follow-up

Subjects are required to stay in the hospital for a minimum of 4 hours post-procedure. Post-procedure assessment must occur during the index procedure hospitalization prior to hospital discharge or at 7 days post index procedure, whichever is sooner. The evaluation must include:

- TTE is required to surveil for pericardial effusion. The study must be performed at a minimum of 4 hours from the end of the procedure (removal of the access sheath).
- A neurological assessment (NIHSS and mRS) to evaluate neuro status of subject. If the
 assessment is indicative of a potential neurological deficit, further evaluation by a boardcertified neurologist or designee (e.g., neurology fellow) must be performed.
- Adverse event assessment

Prior to hospital discharge, research staff should review the follow-up requirements with the subject to ensure compliance with the subsequent follow-up assessment.

9.8 7-day Follow-up + 2 Days (Telehealth Visit)

All subjects must undergo a follow-up assessment on days 7 to 9 post-procedure to enable timely documentation of safety endpoint events.

If the subject has not yet been discharged from the index procedure hospitalization at day 7 post-procedure, the 7-day follow-up may be conducted in-hospital, and no separate telehealth visit is necessary. In-hospital/clinic visit will satisfy the telehealth visit, if appropriate.

The 7-day follow-up assessment must include:

 Questionnaire for Verifying Stroke Free Status (QVSFS). If any question is answered "Yes," a formal neurologic examination and evaluation must be performed by a board-certified neurologist or clinical designee (e.g., neurology fellow).

- Current concomitant medications documentation. If DAPT has been interrupted or terminated, the stop date (and resumption date, if applicable) and the reason for interruption/termination should be recorded.
- Adverse event assessment

9.9 45-day Follow-up ± 7 Days (Telehealth Visit and Imaging)

All subjects will complete an assessment at 45 days (±7 days) post-procedure with imaging (TEE or CT) and clinical evaluation through a minimum of a telehealth visit. The 45-day follow-up visit will include the following assessments:

- Questionnaire for Verifying Stroke Free Status (QVSFS) If any question is answered "Yes," a formal neurologic examination and evaluation must be performed by a board-certified neurologist or clinical designee (e.g., neurology fellow).
- **Imaging evaluation**, preferably TEE, must be performed in all subjects who left the index procedure with an implanted device.
 - Cardiac CT may be used in lieu of TEE to screen for end point findings, e.g., DRT or >3mm Leak.
 - If a Device Related Thrombus is detected, a TEE is required to confirm the finding as soon as possible (recommended assessment within 2 weeks; at latest, 4-6 weeks from date of original study or at the subject's next follow up visit, whichever is first).
 - If a non-trivial leak is noted, a TEE is required to confirm the finding, as soon as possible (recommended assessment within 2 weeks; at latest, 4-6 weeks from date of original study or at the subject's next follow up visit, whichever is first).
 - Note: A trivial leak is one in which filling is incomplete or is seen on only delayed imaging, with a gap that is ≤1mm.
 - If a non-trivial Pericardial Effusion (defined as effusion measuring >10mm) is detected on Cardiac CT, TTE evaluation is required for quantification.
- Current concomitant medications documentation. If DAPT has been interrupted or terminated, the stop date (and resumption date, if applicable) and the reason for interruption/termination should be recorded.
- Adverse event assessment

Prior to concluding the visit, research staff should also review the follow-up requirements with the subject to help ensure study compliance.

NOTE: Subjects who were withdrawn due to no longer meeting eligibility criteria at the time of the index procedure TEE, but never had a procedure attempt, must be followed through 45-days post procedure for telehealth/phone call visits including 7-days and 45-days (imaging not required and protocol mandated medication therapy not required). After the 45-Day follow-up, these subjects will have completed all required study assessments.

9.10 6-month Follow-up (± 30 days) (Telehealth Visit)

All subjects will have a clinical assessment performed via a telehealth visit (at a minimum) at 6 months (± 30 days), to include the following assessments:

- Questionnaire for Verifying Stroke Free Status (QVSFS) If any question is answered "Yes," a formal neurologic examination and evaluation must be performed by a board-certified neurologist or clinical designee (e.g., neurology fellow).
- Current concomitant medications documentation. If DAPT has been interrupted or terminated, the stop date (and resumption date, if applicable) and the reason for interruption/termination should be recorded.
- Assessment for change to monotherapy.
- Adverse event assessment.

Prior to concluding the visit, research staff should also review the follow-up requirements with the subject to help ensure continued study compliance.

9.11 12-Month Follow-up ± 30 Days (Telehealth Visit and Imaging)

All subjects will complete an assessment at 12 months (± 30 days) post-procedure with imaging (TEE) and clinical evaluation through a minimum of a telehealth visit. The 12-month follow-up visit will include the following assessments:

- Questionnaire for Verifying Stroke Free Status (QVSFS) If any question is answered "Yes," a formal neurologic examination and evaluation must be performed by a board-certified neurologist or clinical designee (e.g., neurology fellow).
- **Imaging evaluation**, preferably TEE, must be performed in all subjects who left the index procedure with an implanted device.
 - Cardiac CT may be used in lieu of TEE to screen for end point findings, e.g., DRT or >3mm Leak.
 - If a Device Related Thrombus is detected, a TEE is required to confirm the finding as soon as possible (recommended assessment within 2 weeks; at latest, 4-6 weeks from date of original study or at the subject's next follow up visit, whichever is first).
 - If a non-trivial leak is noted, a TEE is required to confirm the finding, as soon as possible (recommended assessment within 2 weeks; at latest, 4-6 weeks from date of original study or at the subject's next follow up visit, whichever is first).
 - Note: A trivial leak is one in which filling is incomplete or is seen on only delayed imaging, with a gap that is ≤1mm.
 - If a non-trivial Pericardial Effusion (defined as effusion measuring >10mm) is detected on Cardiac CT, TTE evaluation is required for quantification.
- Current concomitant medications documentation. Anticoagulant/antiplatelet therapy per SOC/ investigator decision.
- Adverse event assessment

Prior to concluding the visit, research staff should also review the follow-up requirements with the subject to help ensure study compliance.

